8.4 Safety assessments

8.4.1 Physical examination

Performed as standard physical examination and include the following:

- General appearance
- Head, ears, eyes, nose, throat, neck
- Respiratory system
- Cardiovascular system
- Gastrointestinal system including mouth
- Genito-Urinary system, breasts
- Musculoskeletal system
- Central and peripheral nervous system
- Skin
- Lymph node palpation

The investigator must evaluate the results of the examination and classify the outcome as either:

- Normal or abnormal.
- If abnormal the investigator must:
 - Specify the abnormality
 - Record if the result is clinically significant (Yes/No)
 - If observed before or at Screening: record as Medical History (section [8.2.2](#))
 - If observed after screening: report an AE/SAE (section [12](#))
- Measurements will be reported in the eCRF

8.4.2 Body measurements

Height (cm), at screening

Body Weight (kg), with 1 decimal.

The body weight assessed at each visit will be used for determination of the concizumab dose to be administered until next visit.

Measurements will be reported in the eCRF

8.4.3 Vital signs

Before measurement of vital signs the patient should preferably rest comfortably for at least five minutes and all measurements should, if possible, be performed using the same method and sitting position throughout the trial.

Protocol
 Trial ID:NN7415-4255
 UTN:U1111-1179-3872
 EudraCT no.:2016-000614-29

~~CONFIDENTIAL~~

Date: 28 December 2017
 Version: 4.0
 Status: Final
 Page: 60 of 124

Novo Nordisk

Measurements at visits must be performed prior to any trial product administration unless otherwise specified

- Body temperature (°C)
- Systolic and diastolic blood pressure, sitting (BP) (mmHg)
- Pulse, sitting (beats/min)
- Respiratory rate

Exception: At visit 2, the measurement is also performed after concizumab administration.

The investigator must evaluate the results and classify the outcome as either:

- Normal or abnormal
- If abnormal the investigator must:
 - Specify the abnormality
 - Record if the result is clinically significant (Yes/No)
 - If observed before or at screening: record as concomitant illness (section [8.2.2.](#))
 - If observed after screening: report an AE/SAE (section [12](#))

Measurements will be reported in the eCRF.

8.4.4 Electrocardiogram

The investigator must evaluate the ECG (standard 12 lead) at screening and classify the outcome as either:

- Normal or Abnormal.
- If Abnormal the investigator must:
 - Specify the abnormality
 - Record if the result is clinically significant? (Yes/No)
 - If observed before or at Screening: record as Medical History (Section [8.2.1](#))
 - If observed after screening: report an AE/SAE (Section [12](#))

The ECG results must be dated and signed by the investigator to verify that the data have been reviewed. Outcome will be reported in the eCRF.

8.4.5 Adverse events

Adverse events (AEs) must be reported at each visit in accordance with the procedures outlined in Section [12](#).

8.4.5.1 Medication error

If a medication error is observed during the trial, the following information is required and a specific event form must be completed in the eCRF in addition to the AE form:

- Trial product(s) involved

Protocol
Trial ID: NN7415-4255
UTN: U1111-1179-3872
EudraCT no.: 2016-000614-29

~~CONFIDENTIAL~~

Date:	28 December 2017	Novo Nordisk
Version:	4.0	
Status:	Final	
Page:	61 of 124	

- Classification of medication error
- Whether the patient experienced any adverse event(s) as a result of the medication error
- Suspected primary reason for the medication error

For definition of medication errors, see Section [12.1.4](#).

8.4.5.2 Adverse events requiring additional data collection

For the following AEs additional data collection is required and specific event forms must be completed in the eCRF in addition to the AE form

In case any of these events fulfil the criteria for a serious adverse event, please report accordingly, see Section [12](#).

Injection site reaction

Investigation of injection site reactions will be performed locally at visit 2 based on patient feedback and by following visual inspections of injection sites for concizumab administration:

Symptoms e.g.

- Pain
- Numbness
- Itching
- Burning

Signs e.g.:

- Redness (mm x mm)
- Induration (mm x mm)
- Swelling
- Dimpling
- Macula
- Haematoma
- Bleeding
- Other (visual reactions)

Any injection site reaction symptom (evaluated between visit 2-16) should be recorded in the AE form and the injection site reaction form, see section [12.1.5](#).

A separate AE should be recorded for each injection site reaction symptom. The affected area should also be evaluated for redness and induration in mm using a ruler. To ensure all local injection site assessments are performed at the injection site, the area around the site will be marked with a pen prior to injection.

Protocol
Trial ID:NN7415-4255
UTN:U1111-1179-3872
EudraCT no.:2016-000614-29

~~CONFIDENTIAL~~

Date: 28 December 2017
Version: 4.0
Status: Final
Page: 62 of 124

Novo Nordisk

In the event of a local reaction, additional visual assessments (as described above) will be performed until resolution as judged necessary by the investigator.

Assessment of injection site reactions can be performed at any time, if deemed necessary by the investigator.

Hypersensitivity reaction

If suspicion of a hypersensitivity reaction occurs the patients should be instructed to contact the site staff as soon as possible for further guidance.

All events of hypersensitivity reactions must be reported and the following information must be obtained if available on the hypersensitivity reaction form:

- Signs and symptoms associated with the event
- Time of appearance after administration of trial drug
- Relevant immunological tests performed (See section [8.5.2.7](#))
- Treatment given for the reaction
- Previous history of similar reactions
- Association with the trial product(s)
- Relevant risk factors associated with the event
- Storage condition of the trial product
- Total number of doses, from first day on trial product, up to the time of this event

8.5 Laboratory assessments

An approximate total blood volume of 525 mL will be taken from each patient in the trial. Ports cannot be used for blood sampling.

A laboratory manual will be provided for detailed description of obtaining and processing blood samples.

All laboratory blood samples collected for this trial except for haematology samples are to be shipped for analysis at central laboratories or further distribution to special laboratories. Haematology samples are to be analysed locally.

The laboratory provides results to the trial sites in the units preferred by the trial sites while the results that are transferred to the trial database will always be in international system of units (SI) .

Laboratory reports listing results from centrally analysed samples will be made available for the investigator. Investigator must review and evaluate the results and report AEs for results which are clinical significant. Laboratory reports will where possible indicate normal ranges

Protocol
 Trial ID:NN7415-4255
 UTN:U1111-1179-3872
 EudraCT no.:2016-000614-29

~~CONFIDENTIAL~~

Date:	28 December 2017	Novo Nordisk
Version:	4.0	
Status:	Final	
Page:	63 of 124	

Categorisation of clinical significance for out of range results may not be required for the following laboratory parameters and the investigator is therefore not required to perform a categorisation even though these parameters are listed in the laboratory report: FVIII activity, FVIII inhibitor test, Thrombin generation, TFPI not bound to concizumab, concizumab concentration in plasma, Anti-concizumab binding antibodies, and Total TFPI.

The laboratory equipment may provide analyses not requested in the protocol but produced automatically in connection with the requested analyses according to specifications in the laboratory standard operating procedures. Such data will not be transferred to the trial database, but abnormal values will be reported to the investigator. The investigator must review all laboratory results for concomitant illnesses and AEs and report these according to section [8.2.2](#) and section [12](#).

Only laboratory samples specified in the protocol must be sent to the central laboratory for analysis; if additional laboratory sampling is needed, e.g. to follow up on AEs, this must be done at a local laboratory except for biomarkers and anti-drug antibodies (anti-concizumab IgE antibodies and anti-concizumab binding antibodies).

Laboratory samples will be destroyed no later than at finalisation of the clinical trial report (CTR).

Antibody samples and human bio-samples, if applicable will be stored as described in section [24.2](#). The investigator may not be able to review the results of antibody measurements in relation to AEs as these are often analysed after LPLV.

8.5.1 Laboratory assessments for efficacy

8.5.1.1 Thrombin generation

The Thrombin Generation Assay (TGA) will be performed at all visits (including unscheduled 24 hour PK visit), except visit 3.

The TGA is included as an exploratory PD assessment.

The generation of thrombin is a fundamental part of the haemostatic system, and is a key measurable parameter of the formation of a clot under bleeding or thrombotic conditions. The thrombin burst is crucial for the formation of a stable fibrin clot.

The Calibrated Automated Thrombogram (CAT) method (used by Thrombinoscope BV) will be used to measure thrombin generation (TG). This method uses a slow acting fluorogenic substrate that allows continuous measurement of thrombin generation in double centrifuged citrated plasma.

In this assay set-up thrombin generation is initiated by low-dose tissue factor that is combined with phospholipid. The result is obtained by comparison to a constant known thrombin activity in a parallel non tissue factor initiated sample. The assay has been validated fit-for-purpose.

Protocol
 Trial ID:NN7415-4255
 UTN:U1111-1179-3872
 EudraCT no.:2016-000614-29

CONFIDENTIAL

Date: 28 December 2017
 Version: 4.0
 Status: Final
 Page: 64 of 124

Novo Nordisk

The thrombin generation endpoints are defined, but not limited to,

- The Endogenous Thrombin Potential (ETP) – the area under the curve
- Peak thrombin generation
- Velocity Index

8.5.1.2 Free TFPI

Free TFPI measures TFPI not bound to concizumab. This enzyme-linked immunosorbent assay (ELISA) test will be sampled for at all assessment visits, including unscheduled 24 hour PK visit.

The free TFPI ELISA assay is an enzyme immunoassay measuring levels of TFPI not bound to concizumab from Diagnostica Stago (named and referred to Asserachrom TOTAL TFPI) and will be used for PD assessments.

Free TFPI is included as a PD assessment.

8.5.2 Laboratory assessments for safety

8.5.2.1 Urinalysis

- pH
- Protein
- Glucose
- Bilirubin

This is a semi qualitative measurement which will be performed (locally) at the screening visit by the site by using the appropriate reagent strips for urinalysis. The results will be recorded in the eCRF.

Clinically significant findings must be recorded as:

- Normal or abnormal
 - if abnormal the investigator must:
 - record if the result is clinically significant? (Yes/No)
 - If observed before or at screening: record as concomitant illness (section [8.2.2](#))

8.5.2.2 Haematology

Haematology samples are to be sampled and analysed locally at all visits, except visit 3.

- Haemoglobin
- Erythrocytes (cell count)
- Thrombocytes (Platelet count)
- Leucocytes (cell count)

Protocol
Trial ID: NN7415-4255
UTN: U1111-1179-3872
EudraCT no.: 2016-000614-29

~~CONFIDENTIAL~~

Date: 28 December 2017
Version: 4.0
Status: Final
Page: 65 of 124

Novo Nordisk

- Differential leucocytes cell count
 - Lymphocytes
 - Monocytes
 - Neutrophils
 - Eosinophils
 - Basophils

The investigator must evaluate the results and record the outcome as:

- Normal or abnormal
- If abnormal the investigator must:
 - Specify the abnormality
 - Record if the result is clinically significant (Yes/No)
 - If observed before or at screening: record as concomitant illness (section [8.2.2](#))
 - If observed after screening: report an AE/SAE (section [12](#))

Haematology results are to be entered into the eCRF.

8.5.2.3 Biochemistry

- Creatinine
- Albumin
- Bilirubin; total, direct and indirect)
- Aspartate aminotransferase (AST)
- Alanine aminotransferase (ALT)
- Gamma glutamyltransferase (GGT)
- Alkaline phosphatase
- C-reactive protein (CRP)

The investigator must evaluate the results and record the outcome as:

- Normal or abnormal
- If abnormal the investigator must:
 - Specify the abnormality
 - Record if the result is clinically significant (Yes/No)
 - If observed before or at screening: record as concomitant illness (section [8.2.2](#))
 - If observed after screening: report an AE/SAE (section [12](#))

8.5.2.4 FVIII activity

- FVIII activity (IU/ml)

8.5.2.5 Coagulation parameters

- Fibrinogen

Protocol
 Trial ID: NN7415-4255
 UTN: U1111-1179-3872
 EudraCT no.: 2016-000614-29

~~CONFIDENTIAL~~

Date:	28 December 2017	Novo Nordisk
Version:	4.0	
Status:	Final	
Page:	66 of 124	

- Prothrombin time (PT) including INR
- D-dimer
- Prothrombin fragment 1+2
- Activated partial thromboplastin time (APTT)
- Antithrombin (AT)

The investigator must evaluate the results and record the outcome as:

- Normal or abnormal
- If abnormal the investigator must:
 - Specify the abnormality
 - Record if the result is clinically significant (Yes/No)
 - If observed before or at screening: record as concomitant illness (section [8.2.2](#))
 - If observed after screening: report an AE/SAE (section [12](#))

8.5.2.6 FVIII inhibitor test

The inhibitor level of the patient will be measured by the Nijmegen method at visit 1 (screening).

- FVIII inhibitor titre (BU)

In order to minimise the risk of false negative results, circulating FVIII product levels should be less than 0.05 IU/ml, when sampling for the test. If the patient has received FVIII within 96 hours of screening, the sampling of FVIII-Inhibitor should be postponed until a time period equal to 8 half-lives of the used product has passed (counting from latest treatment).

8.5.2.7 Anti-concizumab antibodies

Sampling will be performed at all visits except at visit 3. Samples will be collected pre-dose at visit 2, 9 and 16.

Assessment of binding antibodies against concizumab (anti-drug antibodies (ADA)) will be performed at specialised laboratories whereas assessment of neutralising antibodies will be performed at Novo Nordisk A/S.

Analysis for ADA will be done as listed in [Table 2-1](#), with a bridging ECL assay (binding ADA assay), using labelled concizumab for antibody capture and detection. If a sample is confirmed positive in the confirmatory assay, the sample is considered antibody positive. Confirmed positive samples will be characterised for binding to IgG backbone, CDR region or the S241P mutation. Furthermore, positive samples will be characterised for neutralising activity using a modified TFPI functionality assay (neutralising ADA assay). All antibody assays are validated according to international guidelines and recommendations.

The following analyses will be available:

Protocol
 Trial ID:NN7415-4255
 UTN:U1111-1179-3872
 EudraCT no.:2016-000614-29

~~CONFIDENTIAL~~

Date:	28 December 2017	Novo Nordisk
Version:	4.0	
Status:	Final	
Page:	67 of 124	

- Anti-concizumab antibody assay
- Specificity assay (Anti-concizumab antibodies cross reacting with IgG4 backbone, CDR region or S241P mutation)
- Anti-concizumab neutralising antibody assay

Samples will be drawn at all visits except at visit 3. The samples will be analysed in batches during the trial and results will be available to the data monitoring committee approximately every third month after the first patient has been dosed (Section [12](#)). Neutralising antibodies will be analysed and reported at the end of trial. A detailed description of the assay methods will be included in the antibody analysis report at the end of the trial.

Investigators will be notified in case their patient is shown to have developed neutralising antibodies against concizumab.

Samples for the determination of anti-drug antibodies collected during the treatment period must be drawn prior to administering trial products.

In the event that a trial patient develops binding ADAs towards concizumab during the course of the trial and has measurable binding ADAs at his End of Trial visit, the patient may attend an ADA follow-up visit. The ADA positive patients will be called for additional visits, e.g. every 4 to 6 weeks, for safety assessment and blood sampling for ADA and PD markers (free TFPI and Thrombin generation). The ADA positive patients will be followed no longer than one year after End of Trial.

Hypersensitivity

If suspicion of a hypersensitivity reaction occurs, patients should be instructed to contact the site staff as soon as possible for further guidance, see Section [12.1.5](#).

In the event of a severe local and/or systemic hypersensitivity reaction possibly or probably related to trial product, blood sampling for assessment of anti-concizumab IgE antibodies as well as anti-concizumab antibodies should be conducted in relation to the reaction and no later than 1-2 weeks after the event. Additional testing may be performed if deemed relevant (e.g. anti-Host Cell Proteins (HCP) antibodies).

In the event of a severe systemic hypersensitivity reaction to trial product it is recommended also to test for tryptase (total and/or mature tryptase) within 3 hours of the reaction. Moreover, a baseline tryptase measurement is necessary 1-2 weeks after the immediate severe hypersensitivity reaction due to individual to individual variation in tryptase baseline concentration.

A follow up visit should be conducted 3-4 weeks post the allergic reaction with repeated blood sampling for assessment of anti-concizumab IgE antibodies as well as anti-concizumab antibodies

Protocol
 Trial ID:NN7415-4255
 UTN:U1111-1179-3872
 EudraCT no.:2016-000614-29

~~CONFIDENTIAL~~

Date:	28 December 2017	Novo Nordisk
Version:	4.0	
Status:	Final	
Page:	68 of 124	

and if possible also at a visit 3 months post the hypersensitivity reaction for assessing the persistence of the IgE response. Tryptase measurements are not required at the follow up visits.

Additionally, basophil activation testing may be performed if deemed relevant. This can be performed using existing samples and/or by analysing the patient's basophil cells from an additional blood sample taken 3-4 weeks and no later than 2 months after the event. Similarly, prick tests and/or intra-dermal tests may be performed if relevant using trial product or components of trial product. Complement may be measured in case of suspicion of immune complex mediated hypersensitivity reactions.

Results from the following additional tests will be reported to Novo Nordisk Safety Operations for inclusion in the ARGUS database and included in the narratives, if measured:

Test to be performed in case of severe hypersensitivity

- Anti-concizumab IgE antibodies
- Anti-concizumab antibodies (additional to scheduled time points)

Additional testing may be performed if deemed relevant e.g

- Anti-Host Cell Proteins (HCP) antibodies
- Anti-HCP IgE antibodies
- Basophil activation results
- Prick test/intra-dermal test
- Complement test results

Furthermore, it is recommended locally to test for

- Tryptase (total and/or mature tryptase)

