6.4 Criteria for premature discontinuation of trial product

The patient may be prematurely discontinued from trial product at the discretion of the investigator due to a safety concern.

The patient must be prematurely discontinued from trial product if the following applies:

1. Included in the trial in violation of the inclusion and/or exclusion criteria
2. Simultaneous participation in another clinical trial of an approved or non-approved investigational medicinal product.
3. Incapacity or unwillingness to follow the trial procedures
4. Anaphylactic reaction
5. Thromboembolic event
6. Event of disseminated intravascular coagulation (DIC)
7. Development of inhibitors to Factor VIII (≥ 0.6 BU)
8. Lack of efficacy due to neutralising antibodies towards concizumab
9. Lack of efficacy defined as ≥ 3 treated sBEs within the previous 12 weeks in patients being treated with the highest dose level (0.25 mg/kg) of concizumab.

See Section [8.1.4](#) for procedures to be performed for patients discontinuing trial product prematurely.

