6.7 Rationale for trial population

The most important reason for choosing the trial population, haemophilia A without inhibitors, is that there is a significant unmet medical need in this patient population for a treatment option which reduces the burden associated with the current care, including small volume s.c. administration instead of i.v. Finally, the trial population reflects the patient population that will be selected in a potential subsequent phase 3 trial in which the efficacy and safety of concizumab is to be confirmed.

Protocol
 Trial ID:NN7415-4255
 UTN:U1111-1179-3872
 EudraCT no.:2016-000614-29

~~CONFIDENTIAL~~

Date:	28 December 2017	Novo Nordisk
Version:	4.0	
Status:	Final	
Page:	40 of 124	

7 Milestones

Planned duration of recruitment period first patient first visit – last patient first visit (FPFV-LPFV):
 4 months

Planned FPFV:	16-Aug-2017
Planned FPFT:	30-Aug-2017
Planned LPFV:	16-Dec-2017
Planned LPLV:	11-Sep-2019

The total duration of concizumab treatment in the trial is 76 weeks for an individual patient enrolled in the trial for concizumab treatment at visit 2.

End of trial is defined as last patient last visit (LPLV).

Recruitment:

The screening and enrolment rate will be followed closely via the interactive web response system (IWRS) in order to estimate when to stop screening. All investigators will be notified immediately when the recruitment period ends, after which no further patients may be screened and the IWRS will be closed for further screening. All patients screened during the recruitment period and found eligible for enrolment can be enrolled within the timelines specified in the flow chart (see Section [2](#)).

Trial registration:

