8.1.10.3 Visit 16 (Assessment visit end of treatment with Concizumab) - Extension part

Visit 16 is to be scheduled on trial day 533 (76 weeks) with a visit window of ± 7 days.

Visit 16 should be scheduled to be conducted at the last day of treatment with concizumab.

Treatment with concizumab must take place after the blood sampling at this visit.

Patients will be asked to complete the PRO questionnaires before any other trial related activities are performed according to section [8.6.1](#);

Protocol
 Trial ID:NN7415-4255
 UTN:U1111-1179-3872
 EudraCT no.:2016-000614-29

~~CONFIDENTIAL~~

Date:	28 December 2017	Novo Nordisk
Version:	4.0	
Status:	Final	
Page:	51 of 124	

- Hemo-TEM
- SF-36v2
- SDS
- TSQM
- H-DAT
- SIAQ-ISRQ

Assessments are to be performed according to [Table 2–1](#) and the assessment results from concomitant medication, vital signs and details of adverse events (AE) must be entered into the eCRF.

Investigator is to perform compliance check of treatment and reporting of bleeding episodes through reviewing collected data from the eDiary.

In the period from visit 16 to visit 17 the patient can be treated with turoctocog alfa (rFVIII) at the discretion of the investigator. Treatment can either be prophylactically and/or treatment of eventual bleeding episodes. Only turoctocog alfa will be provided by Novo Nordisk.

If necessary, a dispensing call must be performed in the IWRS. At the visit the patient will be provided with rFVIII (turoctocog alfa) and injection kits to be able to conduct home treatment until final visit.

The patient will be asked to return all used, partly used and unused concizumab cartridges and turoctocog alfa (FVIII) during the trial as instructed by the investigator. NovoPen 4 must be returned. Drug accountability must be performed at all visits for concizumab and rFVIII (turoctocog alfa) including injection kits, if applicable. Unused sodium chloride syringes should be returned to site at every visit and new sodium chloride syringes should be dispensed to the patient.

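### Mandatory discontinuation for lack of efficacy due to neutralising antibodies (6.4 item 8) has no result to act on, because 8.5.2.7 schedules that assay at end of trial, after the patient's last dose.

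*Protocol*

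**What the plan says.** Section 6.4 lists conditions under which trial product must be stopped. Item 8 is "Lack of efficacy due to neutralising antibodies towards concizumab". Item 9 is a separate stop for three or more treated spontaneous bleeds in 12 weeks, but only "in patients being treated with the highest dose level (0.25 mg/kg) of concizumab".

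Section 8.5.2.7 describes two antibody assays. Binding antibodies are measured at specialised laboratories, whereas "assessment of neutralising antibodies will be performed at Novo Nordisk A/S". On timing it says: "The samples will be analysed in batches during the trial and results will be available to the data monitoring committee approximately every third month". The next sentence treats the neutralising assay separately: "Neutralising antibodies will be analysed and reported at the end of trial". It then promises: "Investigators will be notified in case their patient is shown to have developed neutralising antibodies against concizumab". No time is attached to that promise.

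Section 7 defines end of trial as last patient last visit (LPLV). Section 8.1.10.3 makes visit 16 the last dosing day: "Visit 16 is to be scheduled on trial day 533 (76 weeks) with a visit window of" 7 days either way. Section 8.1.11.1 puts visit 17 on day 589, with up to 7 days earlier allowed.

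**The concern.** Item 8 is a causal criterion. Applying it requires lack of efficacy and also evidence that neutralising antibodies are the reason. The plan assigns that evidence to one assay and schedules the assay for a time when nobody is still being dosed. A mandatory protective rule is therefore written so that its routine input arrives too late.

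Below 0.25 mg/kg, item 8 is the only listed mandatory stop for lack of efficacy. A patient who loses effect through neutralising antibodies meets the escalation trigger in section 5.3.1 like any other non-responder. He may be moved to a higher dose unless other results lead the investigator to hold back. What is at stake is the earlier exit that item 8 was meant to give him.

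**Working it through.** **Inputs (Protocol, version 4.0 text)**

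- Visit 16, last dose: day 533, window 526 to 540 (8.1.10.3).
- Visit 17: day 589, window 582 to 589 (8.1.11.1).
- Follow-up period stated as 8 weeks (5.1).
- End of trial: LPLV (7).
- After premature discontinuation: visit 17 at 8 weeks after the last dose, up to 7 days earlier (8.1.4).

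**Reproducing the plan's figure**

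589 − 533 = 56 days, and 56 / 7 = 8 weeks. This matches the stated follow-up.

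**Gap from last dose to the patient's own visit 17, for a completer**

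- Nominal: 589 − 533 = 56 days.
- Shortest within windows: 582 − 540 = 42 days.
- Longest within windows: 589 − 526 = 63 days.

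For a patient who stops early the gap is 56 − 7 = 49 to 56 days.

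**Both readings of end of trial**

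- If it means the patient's own visit 17, the result comes 42 to 63 days after a completer's last dose.
- If it means LPLV, it cannot come before his own last visit, so 42 days remains the lower bound.

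Neither reading yields a result while he is on treatment.

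**Other routes to a result during treatment**

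- *Three-monthly batches (8.5.2.7).* The neutralising assay has its own sentence and its own time, and the batch results are stated to go to the data monitoring committee.
- *Notification sentence (8.5.2.7).* It has no timing and depends on an assay scheduled for end of trial.
- *Table 2-2, footnote m.* It allows ongoing antibody analysis after clinical signs, with hypersensitivity and immune-related events as examples. Lack of efficacy is not named. Extra samples are kept for characterisation, and no time is given for a neutralising result.
- *Laboratory report (8.5).* It lists binding antibodies, free TFPI, thrombin generation and concizumab concentration, but not neutralising antibodies.
- *Sections 8.5 and 8.5.3.* On reviewing antibody results against adverse events, 8.5 says the analysis often follows LPLV and 8.5.3 says that it does. They differ from each other and from the in-trial batches.

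**The case against.** The best counter-argument is that a patient suspected of item 8 is no longer on a routine path. Footnote m gives examples and not a closed list. Investigators are promised notification without any wording that makes it post-trial. The monitoring committee sees batch results about every three months and can recommend changes (12.8.2, shown only in the version 3 text). Free TFPI and concizumab concentration are sampled through treatment and can reveal loss of exposure or target engagement. Escalation needs the investigator's safety judgement on all available laboratory results (5.3.1), the patient may withdraw at any time (6.5), and item 9 is a backstop at the top dose.

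Most of this stands as mitigation. None of it commits to a neutralising result during dosing, which is what item 8 needs.

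A reader might also infer three stronger things that the documents do not support.

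- *That the planned milestone dates show a longer delay for everyone.* For the last patient, LPLV is essentially his own visit 17. Planned last screening on 16-Dec-2017, plus 14 to 21 days, plus 588 days, gives 10 to 17-Aug-2019. That is 32 to 25 days before the planned LPLV of 11-Sep-2019. The difference is slack in the milestone table and not assay delay.
- *That late testing costs nine bleeds.* A patient starting at 0.15 mg/kg needs at least 3 + 3 + 3 = 9 treated spontaneous bleeds before item 9 applies, because each level counts afresh. But item 8 also requires lack of efficacy first, so nine is not the excess caused by late testing.
- *That the 42 to 63 days measure time on ineffective treatment.* They show only that the result falls after the last dose.

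**Conclusion.** The point holds as a conflict between two stated provisions. Section 6.4 item 8 requires a decision during treatment, and 8.5.2.7 schedules the deciding assay after treatment ends. The defect is yes or no. The day counts establish the order of events and are not a measure of harm.

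Its reach is limited. The number of patients affected is not given and may be small: section 18.1, shown only in the version 3 text, reports no antibodies to concizumab in clinical trials so far. No annualised bleeding rate, sample size, power or alpha figure changes.

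The conclusion assumes that the end-of-trial sentence is the operative schedule for the neutralising assay. If the sponsor intended in-trial testing, that sentence is wrong and needs the same correction. It should be corrected because a mandatory patient-protection rule depends on it and the remedy is cheap.

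**What to change.** In 8.5.2.7, replace the end-of-trial sentence with: *Confirmed binding-positive samples will be tested for neutralising activity with each in-trial batch (about every three months), and the investigator will be notified promptly of a positive result. A full report follows at end of trial.* Align 8.5 and 8.5.3 with this.

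Testing on request when a patient meets the lack-of-efficacy trigger is an optional addition. It depends on assay capacity and turnaround, which the protocol does not give.

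If in-trial testing is not feasible, delete 6.4 item 8 and state that notification is post-trial, so that the protocol does not promise a stop it cannot apply.

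The cost is a few wording changes and some earlier, smaller runs of an assay already planned, on samples already drawn. No visits or blood draws are added. A batch result may still arrive after a first escalation, so the fix narrows the gap without closing it fully.
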